Descriptive statistics will be performed. The primary group for analysis will consist of all subjects who received at least one dose during the double-blind placebo-controlled phase. Analyses will compare change from randomization (visit 3) to end of treatment (visit 7). Tests of equivalence will be performed on primary, secondary and exploratory outcomes, with significance level of p<.05.

Study Procedures:

Refer to the Study Schedule/Flowchart, below.

Number of Subjects: 30 (20 active treatment, 10 placebo group).

Eligibility criteria:

INCLUSION CRITERIA:

- 1. Aged 25-80 at screening. Subjects older than 80 will be allowed at the discretion of the PI.
- 2. Ambulatory (defined as able to ambulate at least 10 meters, with or without assistance).
- 3. Clinical Diagnosis of PD based on the United Kingdom Brain Bank diagnostic criteria for PD.
- 4. At baseline visit (Visit 2) patients must have:
 - a. At least 8 micturitions per 24 hours and

- b. At least 3 urgency episodes per 3-day diary.
- 5. A MoCA score between 19 and 28 (inclusive) at screening. For those on cognitive enhancers (donepezil, rivastigmine, memantine, galantamine) a MoCA score between 19 and 29 (inclusive) at screening.
- 6. Provide informed consent to participate in the study and understand that they may withdraw their consent at any time without prejudice to their future medical care.
- 7. Be cognitively capable, in the opinion of investigator, to understand and provide such informed consent.
- 8. Be cognitively capable to complete the required questionnaires and assessments, OR have a care partner who is willing and capable to assist them in the completion of these tasks.
- 9. Be on a stable regimen of antiparkinson's medications at least 30 days prior to screening, and be expected to remain on a stable dose for the duration of the study.
- 10. If taking cognitive enhancers (donepezil, rivastigmine, memantine, galantamine), must be on stable dose at least 30 days prior to screening, and be expected to remain on a stable dose for the duration of the study.

EXCLUSION CRITERIA:

- 1. Known or suspected alcohol or substance abuse in the preceding 12 months.
- 2. Women who are pregnant or breastfeeding.
- 3. Women of childbearing potential (WOCP) who are not using at least one method of contraception.
- 4. Patients with severe renal impairment ($CL_{cr} \le 29 \text{ mL/min}$, or eGFR ≤ 29 mL/min/1.73 m²), or moderate or severe hepatic impairment (Child-Pugh classes B or C).

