7.0 DATA ANALYSIS AND STATISTICAL METHODS

7.1 Sample size

As this is a pilot study, no formal sample size calculation was performed. For feasibility reasons, a total of 30 participants will be enrolled with 10 in the placebo group and 20 in the active treatment group.

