7.4 Data summary

Data will be collected on case report forms for each participant at each visit and doubleentered into a secure study database. A quality check of data will occur after the first five records and prior to analysis, looking for out-of-range values and inconsistent data. The study statistician will conduct additional quality checks prior to data analyses including consistency between rounds of data entry, checking for duplicate entries, truncation of data, out-of-range values, inconsistent data and amount of missing data. Data discrepancies will be resolved and documented prior to data analysis. Missing data will not be imputed. After quality checks have been completed, a final database will be created with proper formatting and any appropriate mathematical algorithms applied including change from randomization visit (Visit 3).

Descriptive summaries will be generated for all demographic and clinical variables by study visit and treatment group including number, mean, median, standard deviation, minimum and maximum for continuous variables and number and percent for categorical variables. Summaries for change from randomization visit will also be generated. The number and screening/baseline characteristics of withdrawn participants will be recorded.

Subgroups for analyses may include treatment group, time point/study visit, age group and sex. A significance level of 0.05 will be used throughout with no adjustment for multiplicity. Normality will be tested throughout using the Shapiro-Wilk test. All analyses will be conducted on the final dataset in SAS version 9.3 or higher.

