7.4.1 Summary of primary outcome data

The primary objective of this experimental protocol is to assess cognitive tolerability of mirabegron while treating OAB symptoms in patients with PD and CI. The hypothesis is that mirabegron will not impact cognitive impairment. The goal is to demonstrate equivalent cognitive impairment prior to and following treatment with mirabegron as well as change compared to the placebo group. To assess this primary objective, a test of equivalence will be performed using the two one-sided tests approach on change from visit 3 to visit 7 in MoCA total score within groups as well as between the two groups. Normality will be assessed by the Shapiro-Wilk test and the appropriate t-test or non-parametric alternative will be used. The equivalence range will be set at (-2, 2).

Other measures of cognitive impairment will follow similar analyses, but will not be considered the primary endpoint. Equivalence ranges will be determined for each measure based on available literature prior to data analysis.

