7.4.2 Summary of efficacy data

The first secondary objective of this project is to assess the efficacy of mirabegron for treating OAB symptoms in PD with CI. The hypothesis is that participants in the

treatment group will experience improved OAB symptoms compared to placebo group. As this is a superiority objective, a 2-sample t-test or the Mann-Whitney-Wilcoxon test will be used as appropriate to determine significant differences between treatment groups on change in OABQ subscale scores from visit 3 to visit 7. Other measures of OAB symptoms (including PPBC and the average daily values from the diary) will follow similar analyses.

The rest of the secondary objectives are to assess efficacy of mirabegron in PD and the impact of mirabegron on other non-motor symptoms in PD including health related quality of life and excessive daytime sleepiness in PD patients with OAB symptoms and CI. The related hypotheses are that mirabegron will not impact these non-motor symptoms. The goal is to demonstrate equivalent non-motor symptoms prior to and following treatment with mirabegron as well as change compared to the placebo group. Tests of equivalence will be performed using the two one-sided tests approach on change from visit 3 to visit 7 in related variables within groups as well as between the two groups. Equivalence ranges will be determined for each measure based on available literature prior to data analysis.

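### Three equivalence tests serve one primary MoCA objective, and no rule says which result decides

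*Combined protocol and SAP*

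**What the plan says.** Section 7.4.1 gives one hypothesis, that mirabegron will not affect cognitive impairment, and one goal: "The goal is to demonstrate equivalent cognitive impairment prior to and following treatment with mirabegron as well as change compared to the placebo group". The method is TOST on "change from visit 3 to visit 7 in MoCA total score within groups as well as between the two groups". Normality is checked by Shapiro-Wilk, and "the appropriate t-test or non-parametric alternative will be used". One equivalence range, (-2, 2), is given without separating within-arm from between-arm use.

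Section 7.4 adds: "A significance level of 0.05 will be used throughout with no adjustment for multiplicity". Section 7.1 sets 20 mirabegron and 10 placebo patients and says "As this is a pilot study, no formal sample size calculation was performed".

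The synopsis does not settle the matter. Its statistical paragraph says only that "Tests of equivalence will be performed on primary, secondary and exploratory outcomes". Its primary endpoint is a relative mean change in MoCA from Visit 3 to Visit 7, without saying relative to what.

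Sections 7.4.2 and 7.4.3 use the same construction for the other equivalence outcomes: "in related variables within groups as well as between the two groups".

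**The concern.** Three rules are compatible with the text:

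1. Any one result may be quoted as meeting the objective.
2. Within-mirabegron and between-arm must both pass. This is closest to the goal sentence, which names only those two.
3. All three must pass. The methods sentence speaks of groups in the plural, which includes placebo.

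The tests answer different questions. A within-arm change mixes any drug effect with retest gain and disease course over 12 weeks; only the randomized contrast removes these. Retest gain may be modest, because MoCA is also given at screening (section 3.9.1) and three versions exist (section 3.10.1.1), but the documents give no size for it.

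Under rule 1, a between-arm deficit at the margin can be reported as equivalence whenever placebo improves. Under rules 2 and 3 false passes are controlled, but the chance of success differs between the two rules.

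**Working it through.** The plan states no power or derived sample size to reproduce.

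**Inputs from the documents:** n = 20 and 10 (section 7.1); range (-2, 2) (7.4.1); level 0.05, unadjusted (7.4).

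**Assumed:** changes are normal with equal SD in both arms. SD of change is 2 / 2.5 / 3, with 1.5 in brackets. Placebo gain and shared drift are varied, because the documents give neither.

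**Pass condition.** A TOST with each side at 0.05 passes when the 90% CI lies inside (-2, 2), that is, |estimate| + half-width < 2. Half-widths, in units of the observed SD s:

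- within mirabegron: t(0.95, 19)/√20 = 0.387 s
- within placebo: t(0.95, 9)/√10 = 0.580 s
- between arms (pooled variance): t(0.95, 28) × √(1/20 + 1/10) = 0.659 s

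The between-arm interval is 0.659/0.387 = 1.70 times as wide as the within-mirabegron interval. Even with an observed estimate of exactly 0, the between-arm test needs s < 2/0.659 = 3.0, and the within-mirabegron test only s < 2/0.387 = 5.2.

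Pass rates below come from 4,000,000 simulated trials per scenario.

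**(a) True difference at the margin (mirabegron minus placebo = -2)**

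| True change, mirabegron / placebo | Within-mirabegron passes, % | Between-arm passes, % |
|---|---|---|
| -2 / 0 | 5 / 5 / 5 (5) | at most 5 |
| -1.5 / +0.5 | 29 / 22 / 18 (42) | at most 5 |
| -1 / +1 | 70 / 53 / 41 (89) | at most 5 |
| 0 / +2 | 99 / 93 / 78 (100) | at most 5 |

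The two-test and three-test joint rules also pass at most 5% in these scenarios. When placebo improves, a smaller SD raises the within-arm pass rate.

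**(b) No drug effect: chance of success.** The between-arm test alone succeeds in 62 / 29 / 9% (91%), whatever the shared drift.

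| Shared drift | Within-mirabegron and between-arm, % | All three, % |
|---|---|---|
| 0 | 62 / 29 / 8 (91) | 57 / 22 / 5 (90) |
| +0.5 | 60 / 26 / 7 (91) | 47 / 17 / 4 (84) |
| +1 | 45 / 17 / 4 (83) | 23 / 8 / 2 (53) |
| +1.5 | 17 / 6 / 2 (38) | 4 / 2 / 0.5 (10) |

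**(c) Disagreement.** With no effect and no drift, the within-mirabegron and between-arm verdicts differ in 38 / 65 / 71% (9%) of trials. Nearly always the within-arm test passes and the between-arm test is inconclusive; the reverse occurs in 0.6% or less. The conflict can also reverse: if both arms truly decline 2 points (SD 2, no drug effect), between-arm passes 62% and within-mirabegron 5%.

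**(d) Non-parametric route.** This used 40,000 trials with changes rounded to whole points (an assumption). Hodges-Lehmann confidence limits then fall on whole points, so the margin itself becomes a common limit.

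- Requiring limits strictly inside (-2, 2) succeeds in 18 / 3 / 0.5% with no effect.
- Counting -2 and +2 as inside gives about 15 / 12 / 9% false passes at a true -2.
- Two one-sided tie-corrected rank-sum tests succeed in 56 / 25 / 7%, with at most 5% false passes.

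**The case against.** The strongest reply is that the goal sentence joins its two aims with a conjunction, so both are already required. False passes then stay at or below 5%, and table (a) describes a reading the text supports least. This has force: rule 2 is the most natural reading. But the sentence states an aim and gives no success criterion, and the methods sentence also plans a within-placebo test whose role is not given. Even a strictly conjunctive reading leaves a two-test and a three-test rule. At SD 2 and shared drift +1 these succeed in 45% and 23% of trials.

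Several points on weight stand:

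- The large figures in (a) need a placebo gain that the documents do not quantify; at zero gain the within-arm pass rate is 5%.
- Most disagreement in (c) reflects the imprecision of 20 versus 10 patients rather than contradictory evidence.
- The trial is an openly unpowered pilot. Withdrawals are excluded (section 7.3) and not replaced after randomization (7.4.6), so 20 and 10 are ceilings for the analysis. With an assumed 17 and 8 completers, between-arm success with no effect falls to 46 / 16 / 3%.
- A decision rule matters less for the exploratory outcomes in 7.4.3.

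None of this supplies the missing rule, and the plan still sets out to demonstrate equivalence by formal tests.

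**Conclusion.** The concern holds and should be fixed. The gap is in the text and does not depend on any assumed SD: three tests serve one primary objective and no rule links them.

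The size of the consequence does rest on assumptions (normal changes, equal SDs of 1.5 to 3, 20 and 10 analysed). Over that range, at a true difference of -2 split as -1 and +1, the within-mirabegron test passes in 41 to 89% of trials and the randomized comparison in at most 5%. With no effect and no drift, their verdicts differ in 9 to 71%. Requiring both costs almost nothing relative to the between-arm test alone until shared drift reaches about 1 point. Pilot status limits the weight of the conclusion but does not remove the need for a rule.

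**What to change.** State in section 7.4.1 and the synopsis:

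> The single deciding primary analysis is the between-arm difference in MoCA change from Visit 3 to Visit 7 (mirabegron minus placebo). Equivalence is concluded if its two-sided 90% CI lies wholly within (-2, 2). If the non-parametric alternative is used, the same range is tested by two one-sided tie-corrected Wilcoxon rank-sum tests against shifts of -2 and +2, each at one-sided 0.05, and the Hodges-Lehmann shift is reported with its 90% CI. Within-arm changes are reported with CIs as descriptive, with no pass/fail.

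Make the same change for the equivalence tests in 7.4.2 and 7.4.3, each with its own range.

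If the sponsor wishes to keep the formal pre/post claim, state instead that the within-mirabegron and between-arm tests must both pass, and that the within-placebo result is descriptive.

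**Cost.** A few sentences; no extra data or visits. The first option gives up formal pre/post equivalence on mirabegron, which is part of the stated goal. The second keeps it and loses appreciable power only if both arms drift: at SD 2, success falls from 62% to 60% at drift +0.5 and to 45% at +1.

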7.4.2 Summary of efficacy data

The first secondary objective of this project is to assess the efficacy of mirabegron for treating OAB symptoms in PD with CI. The hypothesis is that participants in the

treatment group will experience improved OAB symptoms compared to placebo group. As this is a superiority objective, a 2-sample t-test or the Mann-Whitney-Wilcoxon test will be used as appropriate to determine significant differences between treatment groups on change in OABQ subscale scores from visit 3 to visit 7. Other measures of OAB symptoms (including PPBC and the average daily values from the diary) will follow similar analyses.

The rest of the secondary objectives are to assess efficacy of mirabegron in PD and the impact of mirabegron on other non-motor symptoms in PD including health related quality of life and excessive daytime sleepiness in PD patients with OAB symptoms and CI. The related hypotheses are that mirabegron will not impact these non-motor symptoms. The goal is to demonstrate equivalent non-motor symptoms prior to and following treatment with mirabegron as well as change compared to the placebo group. Tests of equivalence will be performed using the two one-sided tests approach on change from visit 3 to visit 7 in related variables within groups as well as between the two groups. Equivalence ranges will be determined for each measure based on available literature prior to data analysis.

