1.2 Clinical experience with mirabegron: efficacy, safety, and tolerability

Mirabegron efficacy, safety and tolerability were evaluated in three 12-week, double-blind, randomized, placebo-controlled, parallel-group, multicenter clinical trials. Long-

term safety and tolerability were further assessed in one 12-month, double-blind, randomized, active-control, parallel-group, multicenter clinical trial in patients with overactive bladder with symptoms of urinary incontinence and urinary frequency. Entry criteria for each of the four clinical trials required that patients had symptoms of overactive bladder ≥3 months, ≥8 micturitions per day, and ≥3 episodes of urgency with or without incontinence over a 3-day period. ¹⁸⁻²¹ (see Myrbetriq Full Prescribing Information, Appendix 1) It is estimated that over 10,500 subjects have received mirabegron in clinical trials over approximately 10 years, with over 5,500 patients with OAB symptoms having received the drug during Phase II and III clinical trials sponsored by Astellas. ²²

In Phase III clinical trials, mirabegron showed significant efficacy in treating the symptoms of OAB at daily doses of 25, 50, and 100 mg. Specifically, improvements were demonstrated in micturition frequency, urgency incontinence, and urgency. At daily doses of 50 and 100 mg of mirabegron, sustained improvements were attained as early as during week 4. Among responders, the magnitude of the therapeutic effect measured an at least 50% reduction in mean daily (24h) number of incontinence episodes, and in the proportion of patients with 8 daily (24h) micturitions or less. Of importance to the present discussion, patients aged 65 or older benefited from mirabegron 50 and 100 mg. Long-term clinical trials of up to 12 months demonstrated good long term safety and tolerability. The most common adverse events included hypertension, nasopharyngitis, and urinary tract infection. When looking specifically at anticholinergic side effects, the incidence of dry mouth was similar to placebo, and was between three and fivefold less than for tolterodine extended release 4 mg.

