3.9.6 High-dose phase maintenance visit (Visit 6; Day 42)

The purpose of this visit is to establish interim overall tolerability of the medication, medication compliance, and obtain interim measures for analysis.

- Concomitant medications
- Adverse events
- Study drug compliance
- OABQ
- 3-day VD assessment
- PPBC
- Study drug dispense

At the conclusion of Visit 6, subjects will be dispensed mirabegron 25 mg tablets or matching placebo. Study drug will be administered in the form of 2 mirabegron 25 mg, matching placebo tablets daily (placebo arm) or 2 mirabegron 25 mg tablets daily (active treatment arm). Thus all subjects will continue to receive 2 identical looking tablets daily. Sufficient study drug will be dispensed to last until the end of treatment visit (Visit 7).

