3.10.2 Procedures related to secondary end points

3.10.2.1 Overactive Bladder Questionnaire (OABQ – Appendix III)

Overactive bladder (OAB) is characterized by symptoms of urinary frequency and urgency, with and without incontinence. The Overactive Bladder Questionnaire³³ (OABQ) is a 33-item, self-administered instrument that contains a symptom bother scale (8 items to be administered during visits 1, 3, 5, 6, and 7) and a health-related quality of life scale (HRQL-to be administered during visits 3 and 7), pertaining to OAB symptoms

impact on HRQL. The OABQ was developed from an initial version of 62 items to its final form and has been shown to be a valid and reliable instrument in distinguishing normal from clinically diagnosed continent and incontinent patients. In addition to measuring the severity of symptom bother, the OABQ is also useful in quantifying the negative impact of both continent and incontinent symptoms on HRQL. This instrument has been used as an efficacy outcome in the pivotal randomized clinical trials of mirabegron, and the drug's efficacy was indeed accurately reflected in the instrument. The OABQ has also been studied and found useful in PD. ³⁴

3.10.2.2 3-Day Voiding Diary (Appendix IV)

A 3-day voiding diary will be implemented to collect additional efficacy measures of average daily incontinence episodes, micturition frequency, and volume voided per micturition. Subjects will be trained in the diary completion. A toilet hat will be supplied for volume measurement. Subjects are instructed to record the times of every voiding event during three consecutive days; amount voided with each event; instances of leaking including incontinence; whether there was associated urge to void with any voiding event; and, whether they had to get out of bed to void.

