Interval								
p-value		0.003#		0.026#		0.005#	0.001#	
Number of Mic								
n	480	473	433	425	415	410	426	
Baseline	11.71	11.65	11.51	11.80	11.48	11.68	11.66	
(mean)	-							
Change from baseline	l				1			
(adjusted	-1.34	-1.93	-1.05	-1.66	-1.18	-1.65	-1.60	
mean [†])	l							
Difference								
from	l				1			
placebo		-0.60		-0.61		-0.47	-0.42	
(adjusted	l				1			
mean [†])					 			
95%	l				1	(000 013)	(0.76 0.00)	
Confidence Interval	-	(-0.90, -0.29)	-	(-0.98, -0.24)		(-0.82, -0.13)	(-0.76, -0.08)	
p-value	 	<0.001#		0.001#	+	0.007#	0.015#	
Volume Voide	d (mI) ner			0.001#		0.007#	0.015#	
n	480	472	433	424	415	410	426	
Baseline								
(mean)	156.7	161.1	157.5	156.3	164.0	165.2	159.3	
Change from								
baseline	12.3	24.2	7.0	18.2	8.3	12.8	20.7	
(adjusted	12.5	24.2	7.0	10.2	8.3	12.0	20.7	
mean [†])								
Difference	l							
from	l	11.0		11.1		4.6	12.4	
placebo (adjusted	-	11.9		11.1	-	4.0	12.4	
(adjusted mean [†])	l							
95%					+			
Confidence		(6.3, 17.4)		(4.4, 17.9)		(-1.6, 10.8)	(6.3, 18.6)	
Interval		,,		,,		,,,	, , , , , ,	
p-value		< 0.001#		0.001#		0.15	<0.001#	

Week 12 is last observation on treatment

Myrbetriq 25 mg was effective in treating the symptoms of OAB within 8 weeks, and Myrbetriq 50 mg was effective in treating the symptoms of OAB within 4 weeks. Efficacy of both 25 mg and 50 mg doses of Myrbetriq was maintained through the 12-week treatment period.

 $[\]dot{\uparrow}$ Least squares mean adjusted for baseline, gender, and geographical region

^{*}For incontinence episodes per 24 hours, the analysis population is restricted to patients with at least 1 episode of incontinence at baseline.
#Statistically significantly superior compared to placebo at the 0.05 level with multiplicity adjustment

Figures 3 through 8 show the co-primary endpoints, mean change from baseline (BL) over time in number of incontinence episodes per 24 hours and mean change from baseline over time in number of micturitions per 24 hours, in Studies 1, 2 and 3.

Figure 3. Mean (SE) Change from Baseline in Mean Number of Incontinence Episodes per 24 Hours –Study 1

[figure not shown]

Figure 4. Mean (SE) Change from Baseline in Mean Number of Micturitions per 24 Hours - Study 1

[figure not shown]

Figure 5. Mean (SE) Change from Baseline in Mean Number of Incontinence Episodes per 24 Hours - Study 2

[figure not shown]

Figure 6. Mean (SE) Change from Baseline in Mean Number of Micturitions per 24 Hours - Study 2

[figure not shown]

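### The bladder efficacy tests use only the unadjusted Visit 3 to Visit 7 change, although Visit 6 and an earlier pre-treatment reading are collected and could tighten the estimates at no extra patient burden

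*Combined protocol and SAP*

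**What the plan says.** Section 7.4.2 sets the efficacy test: a two-sample t-test or Mann-Whitney-Wilcoxon test for "significant differences between treatment groups on change in OABQ subscale scores from visit 3 to visit 7". It adds: "Other measures of OAB symptoms (including PPBC and the average daily values from the diary) will follow similar analyses". The Statistical Analysis paragraph of the Synopsis gives the same two time points for analyses generally. No covariate and no repeated-measures model is mentioned.

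The schedule collects more than this:

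- **Diary and PPBC:** Visits 2, 3, 5, 6 and 7 (Table 1; PPBC also at Visit 8).
- **OABQ symptom bother** (Section 3.10.2.1): "8 items to be administered during visits 1, 3, 5, 6, and 7".
- **OABQ HRQL scale** (same section): "HRQL-to be administered during visits 3 and 7". Table 1 marks the OABQ as a whole at Visits 1, 3, 5, 6 and 7 without separating the two scales.

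Section 3.9.6 says that Visit 6 is held partly to "obtain interim measures for analysis". Section 7.4 provides descriptive summaries by visit and group, and lists study visit among possible subgroups. It names no test that uses Visits 1, 2, 5 or 6.

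**The concern.** Visit 6 (Day 42) falls 28 days after escalation at Day 14, and Table 4 puts Visits 6 and 7 on the same two-tablet step. The appended label reports that "Myrbetriq 50 mg was effective in treating the symptoms of OAB within 4 weeks", and Section 1.2 says that at 50 and 100 mg "sustained improvements were attained as early as during week 4". Visit 6 is therefore a plausible second look at the escalated dose. The earlier pre-treatment value (Visit 2 for diary and PPBC, Visit 1 for symptom bother) is a natural second covariate.

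The sample size was fixed at 30 for feasibility (Section 7.1), so the choice of analysis is the main remaining lever on precision. Under the plan, each subject's efficacy result rests on one reading before treatment and one after. A subject who stays in the study but misses Visit 7 contributes nothing to the test, even with a valid Visit 6 value.

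**Working it through.** **The plan's own figure.** There is none. Section 7.1 reports no sample size calculation, and the documents give no SD or between-visit correlation for these outcomes in this population.

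**Inputs.** 10 placebo and 20 active (Section 7.1); alpha 0.05 (Section 7.4), taken as two-sided; visit days from Table 1. Assumed: equal variance at every visit, and correlations r_bp (pre-treatment with on-treatment), r_pp (Visit 6 with Visit 7) and r_bb (between the two pre-treatment visits).

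**Formulas**, in units of the single-visit variance:

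- Planned change, V7 − V3: 2(1 − r_bp)
- Mean(V6, V7) − V3: (1 + r_pp)/2 + 1 − 2r_bp. The cut against the plan is (1 − r_pp) / [4(1 − r_bp)].
- V7 adjusted for V3: 1 − r_bp²
- Full model, mean(V6, V7) adjusted for both pre-treatment values: (1 + r_pp)/2 − 2r_bp²/(1 + r_bb)

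Under serial decay the correlations differ by spacing, so the variances were taken from the full visit correlation matrix.

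**Two worked cases**

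- All correlations 0.5: planned 1.00; with V6 0.75 (−25%); V7 adjusted for V3 0.75 (−25%); full model 0.75 − 0.50/1.5 = 0.417 (−58%).
- r_bp = 0.6, r_pp = r_bb = 0.8: planned 0.80; with V6 0.90 + 1 − 1.20 = 0.70 (−12.5%); V7 adjusted for V3 0.64 (−20%); full model 0.90 − 0.72/1.8 = 0.50 (−37.5%).

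**Variance cut against the planned test, over the assumed ranges**

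| Correlation pattern | Add V6 to change score | Adjust V7 for V3 only | Full model |
|---|---|---|---|
| Compound symmetry, r 0.4–0.8 | 25% | 10–30% | 53–61% |
| Block: r_bp 0.4–0.6, r_pp and r_bb 0.6–0.8 | 8–25% | 20–30% | 37.5–56% |
| Serial decay, 0.5–0.8 per 42 days | 33–36% | 18–37.5% | 47–59% |

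Adjusting Visit 7 for both pre-treatment values instead of Visit 3 alone raises the compound-symmetry figure at r = 0.4 to 36%: 1 − 2(0.16)/1.4 = 0.771, against 1.2. So baseline adjustment at Visit 7 alone is worth about 10–36% for r_bp of 0.4–0.8.

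These are large-sample figures. Under normality, estimating two slopes from 30 subjects costs about 2/(30 − 2 − 3) = 8% in variance. That moves the full-model range to 1 − 0.625 × 1.08 = 32.5% at the low end and 1 − 0.393 × 1.08 = 58% at the high end.

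**What a cut buys at 10 versus 20** (noncentral t, planned change-score SD = 1)

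| Variance | Power at a difference of 0.8 | Difference with 80% power |
|---|---|---|
| As planned | 51% | 1.12 |
| −25% | 63% | 0.97 |
| −50% | 81% | 0.79 |

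**Break-even for averaging.** Suppose the Visit 6 effect is a fraction f of the Visit 7 effect. The averaged effect is then (1 + f)/2 of the Visit 7 effect. With a variance cut c, averaging helps only if (1 + f)/2 > √(1 − c), that is f > 2√(1 − c) − 1. For c = 25%, f must exceed 2 × 0.866 − 1 = 0.73. For c = 8%, it must exceed 2 × 0.959 − 1 = 0.92.

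**Power at the label's micturition effects** (50 mg versus placebo, label Table 3). Implied SD = (CI width / 3.92) / √(1/n₁ + 1/n₂): Study 1 2.40, Study 2 2.76, Study 3 2.52. With differences of 0.60, 0.61 and 0.42, power at 10 versus 20 is 7–10%. After a 48% variance cut it is 9–14%.

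**The case against.** **The planned test is legitimate.** It is prespecified, and its baseline-to-end-of-treatment form matches the Week 12 endpoint of the pivotal trials described in the label. This stands: nothing here makes the test invalid.

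**25% is not a floor.** A reader might infer that Visit 6 always saves at least a quarter of the variance. That holds under compound symmetry, but Visits 6 and 7 share the on-treatment phase and may correlate more with each other than with Visit 3. The saving in a change score can then fall to 8%. This stands.

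**The plateau is not shown.** A reader might infer that Visits 6 and 7 measure the same settled effect. The label says that an effect is present within 4 weeks, not that it is complete, and it describes general OAB patients. The OABQ asks about the past 4 weeks (Appendix III), so at Visit 6 it covers Days 14–42, the period of onset. Nor is every subject on two tablets: the Synopsis lets some remain on one, and Section 6.1.8 allows one reduction. This stands as a reason to report Day 84 as well as the average. It does not argue against baseline adjustment, which leaves the Day 84 target unchanged.

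**The data are not discarded.** Section 7.4 summarises them by visit. The accurate statement is that they enter no specified test.

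**The fix does not rescue power.** At the label's micturition effects, power remains about 9–14%. The label intervals come from means already adjusted for baseline, gender and region, so the implied SDs probably flatter the planned unadjusted test. This stands.

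**Withdrawals.** Section 7.3 excludes withdrawn participants from analyses, so a change to Section 7.4.2 alone would not bring in their Visit 6 values. Section 3.9.7 also asks early-termination subjects to complete the Visit 7 procedures. The recovery of data is therefore smaller than it first looks.

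**Conclusion.** The point holds as an efficiency improvement on a secondary objective of a pilot, not as an error. For symptom bother, diary and PPBC, the plan tests the least precise of the available contrasts.

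The full model cuts variance by about 37–61% below the planned test before the small-sample cost of the covariates. Confidence intervals would then be √0.63 = 0.79 to √0.39 = 0.62 times as wide. A substantial part of this comes from baseline adjustment alone, which needs no assumption about when the effect settles. These figures rest on equal variances and on assumed correlations; the documents supply none.

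The documents do not support the stronger inferences that Visit 6 alone guarantees a 25% saving, that Visits 6 and 7 share a proven plateau, or that the trial would become adequately powered for micturition frequency. The HRQL items gain nothing from extra visits, because by Section 3.10.2.1 none are collected.

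**What to change.** In Section 7.4.2, before unblinding:

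1. Analyse symptom bother, diary averages and PPBC with a mixed model on Visits 6 and 7. Use the Visit 3 value and the earlier pre-treatment value (Visit 2 for diary and PPBC, Visit 1 for symptom bother) as covariates. The earlier value should enter as a covariate and not be averaged into the baseline, because it precedes the placebo run-in and Visit 2 also determines diary eligibility. Leave Visit 5, the low-dose phase, out of the average.
2. From the same model, report the Visit 6–7 average effect and the Day 84 effect, and state in advance which is the main result.
3. Keep a rank-based fallback for non-normal outcomes and for PPBC, a single six-category item.
4. For the HRQL subscales, adjust the Visit 7 comparison for Visit 3 only. Reconcile Section 3.10.2.1 with Table 1 on when the HRQL items are given.
5. If Visit 6 data from withdrawn subjects are to be used, amend Section 7.3 to match.

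The cost is SAP wording and modest programming, with no new visit or procedure. If the average is named as the main result, it describes Days 42–84 and is diluted where the Visit 6 effect is well below the Visit 7 effect. Naming Day 84 avoids this but keeps mainly the baseline-adjustment gain (about 10–36%).
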